13.6.2. Asthma Control Test

Subjects with a medical history of asthma will take an Asthma Control Test (ACT) at Screening, Baseline, Week 4, Week 8, Week 12 and Week 16 of the Initial Period and at Week 20, Week 24, Week 28, Week 32, Week 36, Week 40, Week 44, and Week 48 of the Maintenance Period, as well as at Early termination visit, and Follow-up.

The ACT is designed for adults and adolescents 12 years or older, and is composed of 5 questions. For each question, the subject will choose the best answer out of 5 possible answers. The test provides a numerical score ranging from 5 to 25 to assess asthma control; a higher score indicates better asthma control while a score of 19 or less indicates the subject's asthma may not be under control.

Subjects with a new (de novo) diagnosis of asthma during the trial will take the ACT beginning at the visit the diagnosis was first confirmed and at all subsequent study visits thereafter.

ACT total score (absolute values and change from Baseline) will be summarized as a continuous variable (scheduled visits only) for the Initial Treatment Period and the Maintenance Period.

The number and percentage of subjects with an ACT score ≤ 19 will be summarized (scheduled visits only) for the Initial Period and the Maintenance Period.

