8.3.3 Exclusion Criteria

Subjects will be excluded from the study if 1 or more of the following criteria are applicable:

1. Body weight < 30 kg.
2. Subjects meeting 1 or more of the following criteria at screening or baseline:
 - 2a. Had an exacerbation of asthma requiring hospitalization in the preceding 12 months.
 - 2b. Reporting asthma that has not been well-controlled (ie, symptoms occurring on > 2 days per week, nighttime awakenings 2 or more times per week, or some interference with normal activities) during the preceding 3 months.
 - 2c. ACT \leq 19 (only for subjects with a history of asthma).
 - 2d. PEF < 80% of the predicted value.

CONFIDENTIAL

3. Subjects with a current medical history of chronic obstructive pulmonary disease and/or chronic bronchitis.
4. Cutaneous infection within 1 week before the baseline visit, any infection requiring treatment with oral or parenteral antibiotics, antivirals, antiparasitics, or antifungals within 2 weeks before the baseline visit, or any confirmed or suspected COVID-19 infection within 2 weeks before the screening or baseline visit. Subjects may be rescreened once the infection has resolved. Resolution of COVID-19 infection can be confirmed by recovery assessment methods, as described in Section 8.3.4.2.
Note: Subjects with chronic, stable use of prophylactic treatment for recurrent herpes viral infection can be included in this study.
5. Requiring rescue therapy for AD during the run-in period or expected to require rescue therapy within 2 weeks following the baseline visit.
6. Positive serology results (hepatitis B surface antigen [HBsAg] or hepatitis B core antibody [HBcAb], hepatitis C antibody, or human immunodeficiency virus [HIV] antibody) at the screening visit.
Note: Subjects with a positive HBcAb and a negative HBsAg can be included in this clinical study if hepatitis B surface antibody is positive (considered immune after a natural infection).
7. Having received any of the following treatments in Table 6 within the specified timeframe before the baseline visit:

Table 6: Prior Treatments

Treatment(s)	Timeframe
Coal tar products	2 weeks
Topical PDE-4 inhibitor	2 weeks
Non-authorized TCS	2 weeks
Topical medications, including authorized TCS/TCI, with occlusive dressings (eg, wet wraps)	2 weeks
Systemic corticosteroids (corticosteroid inhalers are permitted)	4 weeks
Phototherapy or tanning beds	4 weeks

CONFIDENTIAL

Treatment(s)	Timeframe

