13.6. Respiratory Assessments

13.6.1. Respiratory Examination and PEF Testing

A respiratory examination consisting of questions regarding medical history of asthma, wheeze, dyspnea, and cough, will be performed for all subjects at Screening, Baseline, Week 4, Week 8, Week 12 and Week 16 of the Initial Period and at Week 20, Week 24, Week 28, Week 32, Week 36, Week 40, Week 44, and Week 48 of the Maintenance Period, as well as at Early termination visit, and at Follow-up.

Respiratory examination questionnaire results will be listed on the Safety population.

PEF testing will be performed for all subjects at Screening, Baseline, Week 4, Week 8, Week 12 and Week 16 of the Initial Period and at Week 20, Week 24, Week 28, Week 32, Week 36, Week 40, Week 44, and Week 48 of the Maintenance Period, as well as at Early termination visit, and at Follow-up.

This document is confidential.

PEF (absolute values and change from Baseline; and change from Week 16 for the Maintenance Period) will be summarized as a continuous variable (scheduled visits only) for the Initial Period and the Maintenance Period. PEF will be summarized separately for the subset of subjects with, and without, a history of asthma.

The number and percentage of subjects with PEF < 80% will be summarized by treatment group, visit (scheduled visits only), and medical history of asthma (with and without history of asthma) for the Initial Treatment Period and the Maintenance Period.

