17.2.5.2. Table Conventions

- Units will be included where available
- If the categories of a parameter are ordered, then all categories between the maximum and minimum category are presented in the table, even if n=0 for all treatment groups in a given category that is between the minimum and maximum level for that parameter. For example, the frequency distribution for symptom severity would appear as:

Severity Rating	n
severe	0
moderate	8
mild	3

Where percentages are presented in these tables, zero percentages will not be presented and so counts of 0 will be presented as 0 and not as 0 (0%).

This document is confidential.

- If the categories are not ordered (e.g., Medical History, Reasons for Discontinuation from the Study, etc.), then only those categories for which there is at least 1 subject represented are included.
- An Unknown or Missing category are added to each parameter for which information is not available for 1 or more subjects.
- Unless otherwise specified, the estimated mean, median, Q1 and Q3 for a set of values are printed out to 1 more significant digit than the original values, and standard deviations are printed out to 2 more significant digits than the original values. The minimum and maximum should report the same significant digits as the original values. Missing descriptive statistics or p-values which cannot be estimated are reported as “-”.
- Percentage values are printed to one decimal place, in parentheses with no spaces, one space after the count (e.g., 7 (12.8%), 13 (5.4%)). Pre-determine how to display values that round down to 0.0. A common convention is to display as '<0.1', or as appropriate with additional decimal places. Unless otherwise noted, for all percentages, the number of subjects in the analysis population for the treatment group who have an observation will be the denominator. Percentages after zero counts should not be displayed and percentages equating to 100% are presented as 100%, without decimal places.
- Tabular display of data for medical history, prior/concomitant medications, and all tabular displays of adverse event data are presented by the body system, treatment class, or SOC. The body system, drug class and SOC are displayed in alphabetically order. Within body system, drug class and SOC, preferred term will be display in descending frequency. If incidence for more than 1 preferred term is identical, they should then be sorted alphabetically.

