	14.3.4.4.5	Shift from Maintenance Baseline in Physical Examination - Maintenance Period	Enrolled Safety Subjects in Maintenance Period Population
	14.3.4.4.6	Summary of Respiratory Assessments – Peak Expiratory Flow (PEF) – Initial Period	Safety Population
	14.3.4.4.7	Summary of Respiratory Assessments – Peak Expiratory Flow (PEF) – Maintenance Period	Enrolled Safety Subjects in Maintenance Period Population
	14.3.4.4.8	Summary of Respiratory Assessments – Peak Expiratory Flow (PEF) for Subjects with Asthma History – Initial Period	Safety Population
	14.3.4.4.9	Summary of Respiratory Assessments – Peak Expiratory Flow (PEF) for Subjects with Asthma History – Maintenance Period	Enrolled Safety Subjects in Maintenance Period Population
	14.3.4.4.10	Summary of Respiratory Assessments – Peak Expiratory Flow (PEF) for Subjects without Asthma History – Initial Period	Safety Population
	14.3.4.4.11	Summary of Respiratory Assessments – Peak Expiratory Flow (PEF) for Subjects without Asthma History – Maintenance Period	Enrolled Safety Subjects in Maintenance Period Population
	14.3.4.4.12	Summary of Peak Expiratory Flow (PEF) < 80% of Predicted Value – Initial Period	Safety Population
	14.3.4.4.13	Summary of Peak Expiratory Flow (PEF) < 80% of Predicted Value - Maintenance Period	Enrolled Safety Subjects in Maintenance Period Population

This document is confidential.

Header	Table Number	Name	Analysis Set
	14.3.4.4.14	Summary of Asthma Control Test (ACT) and Proportion of ACT <= 19 – Initial Period	Safety Population
	14.3.4.4.15	Summary of Asthma Control Test (ACT) and Proportion of ACT <= 19 – Maintenance Period	Enrolled Safety Subjects in Maintenance Period Population
	14.3.4.4.16	Summary of Immunogenicity - Anti-drug Antibody (ADA) and Neutralizing Antibody - Initial Period	PK Population
	14.3.4.4.17	Summary of Immunogenicity - Anti-drug Antibody (ADA) and Neutralizing Antibody - Maintenance Period	Enrolled PK Subjects in Maintenance Period Population
14.3.4.5		Extent of Exposure and Treatment Compliance	
	14.3.4.5.1	Summary of Exposure to Study Drug - Initial Period	Safety Population
	14.3.4.5.2	Summary of Exposure to Study Drug - Maintenance Period	Enrolled Safety Subjects in Maintenance Period Population

This document is confidential.

20. Index of Figures

Header	Figure Number	Name	Analysis Set
14		Figures	
14.1		Demographic Data Summary Tables	
14.1.1		Subject Disposition	

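### The by-visit ACT score and percentage with ACT ≤ 19 pool asthma-history subjects with newly diagnosed subjects who join after randomization, so the denominator changes over time and can differ by arm

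*SAP*

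**What the plan says.** SAP 13.6.2 defines two routes into the ACT data.

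- History route: "Subjects with a medical history of asthma will take an Asthma Control Test (ACT) at Screening, Baseline" and at each scheduled visit after that. Protocol 8.3.3, criterion 2c, excludes a score of 19 or less at screening or baseline, and this applies "only for subjects with a history of asthma".
- De novo route: subjects without a history who are diagnosed during the trial "will take the ACT beginning at the visit the diagnosis was first confirmed and at all subsequent study visits thereafter".

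For the analysis, 13.6.2 summarizes the total score (absolute and change from Baseline) and adds: "The number and percentage of subjects with an ACT score ≤ 19 will be summarized (scheduled visits only"), for each period. It names no subset. The Index of Tables (SAP section 19) lists one ACT table per period. Table 14.3.4.4.14 is "Summary of Asthma Control Test (ACT) and Proportion of ACT <= 19 – Initial Period", and 14.3.4.4.15 is its Maintenance Period counterpart.

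Under the table conventions in SAP 17.2.5.2, unless otherwise noted, "the number of subjects in the analysis population for the treatment group who have an observation will be the denominator".

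PEF is handled differently. SAP 13.6.1 states: "PEF will be summarized separately for the subset of subjects with, and without, a history of asthma". The percentage with PEF below 80% is also to be given by asthma history, and the index carries separate PEF tables with and without history (14.3.4.4.8 to 14.3.4.4.11).

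**The concern.** A subject without a history of asthma has an ACT score only after developing asthma on study. The set behind each visit's percentage is therefore partly defined by a safety outcome that occurs after randomization. It is not a fixed cohort, and the arms are not protected by randomization at any visit after Baseline.

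The question that ACT is best placed to answer is whether control worsens in subjects who already have asthma. That is also where the earlier signal lay: Protocol 6.2.3 and 6.3 report phase 2b asthma flares in subjects with pre-existing asthma of 1.8%, 3.6%, 12.3% and 17.5% on placebo, 10 mg, 30 mg and 90 mg. As specified, the plan produces no by-visit percentage with ACT ≤ 19 for that group alone. Its figure mixes control in existing asthma with the occurrence of new asthma, which is already counted as an adverse event of special interest (AESI).

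**Working it through.** **Step 1. Who contributes to each row**

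| Row of the ACT table | History subjects | De novo subjects |
|---|---|---|
| Absolute score | every visit | from diagnosis |
| % with ACT ≤ 19 | every visit | from diagnosis |
| Change from Baseline | every post-baseline visit | none |

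The last row follows from SAP 8.2: Baseline is the latest valid value before the first injection, and de novo subjects have no ACT then. SAP 13.6.2 names no change from Week 16, whereas 13.6.1 does so for PEF. If Week 16 were used as the reference in the Maintenance Period, subjects diagnosed by Week 16 would enter that row too.

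**Step 2. Effect of pooling at one visit**

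Let H and D be the history and de novo subjects with an ACT, and p and q their respective proportions with ACT ≤ 19.

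- Pooled proportion = (H·p + D·q) / (H + D)
- Shift from pooling = pooled − p = [D / (H + D)] × (q − p)

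The sign is the sign of q − p. The weight D / (H + D) grows as cases accrue and differs by arm if incidence differs.

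**Step 3. Inputs**

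The plan states no ACT rate, no share with asthma history and no de novo rate, so there is no figure of its own to reproduce. From the documents: about 750 subjects at 2:1, hence 500 and 250. Everything else below is assumed.

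**Step 4. Worked example**

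Assume 20% with a history, p held at 10%, and de novo asthma in 0.5% (nemolizumab) and 0.125% (placebo) of no-history subjects per visit interval, over four intervals to Week 16.

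- Nemolizumab: H = 500 × 0.20 = 100; D = 400 × 0.02 = 8.
- Placebo: H = 250 × 0.20 = 50; D = 200 × 0.005 = 1.

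Pooled percentage at Week 16, against a true 10.0% in history subjects in both arms:

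| q | Nemolizumab | Placebo |
|---|---|---|
| 50% | (10 + 4)/108 = 13.0% | (5 + 0.5)/51 = 10.8% |
| 10% | (10 + 0.8)/108 = 10.0% | (5 + 0.1)/51 = 10.0% |
| 5% | (10 + 0.4)/108 = 9.6% | (5 + 0.05)/51 = 9.9% |

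With q = 50%, the nemolizumab figure climbs 10.0, 10.8, 11.5, 12.3, 13.0% over Weeks 0, 4, 8, 12 and 16, although nothing changes in the history subjects.

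**Step 5. Range**

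Assume a history share of 15% or 30%, cumulative de novo asthma in 2% (nemolizumab) and 0.5% (placebo) of no-history subjects, p from 5% to 20%, and q from 5% to 80%.

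- Shift on nemolizumab: −1.5 to +7.6 points.
- Shift on placebo: −0.4 to +2.1 points.
- Between-arm difference due to pooling alone: −1.1 to +5.6 points.

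The upper end is 15% history, p = 5%, q = 80%: 8.5/83.5 × 0.75 = 7.6 points against 1.06/38.56 × 0.75 = 2.1 points. The lower end is 15% history, p = 20%, q = 5%.

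**Step 6. Which sign is more likely**

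At the diagnosis visit, q > p is plausible. Subjects without a history are referred because of signs, symptoms or declining respiratory assessments (Protocol 9.2.9.4), and the ACT covers the past four weeks (Protocol Appendix 12). History subjects, in contrast, start at about 0% because of the entry criterion. No document says that q stays above p at later visits.

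**The case against.** A reader might go further and infer that the ACT ≤ 19 rate must rise with time on drug, most of all in the arm with more new asthma. The documents do not support that.

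- Steps 2 and 4 show that the shift can be positive, zero or negative. When q is below p, the arm with more new asthma falls most.
- Testing starts when the diagnosis is confirmed, after specialist referral, so a first score need not be poor.
- History subjects start near 0% by eligibility and can only stay there or rise, in both arms. A rise over time is therefore expected without any late entry and cannot be put down to pooling.
- The phase 2b signal concerned pre-existing asthma. New asthma is named as a potential risk, but no rate by arm is given, so unequal accrual is an assumption.

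These points stand, and they limit the claim to a possible distortion of unknown sign.

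The other side can also say that the change-from-Baseline row is in effect history-only, that n is shown for continuous summaries (SAP 8.1), and that new or worsening asthma is covered by the AESI tables, the adjudicated events and listings 16.2.8.2.7 and 16.2.8.2.8. This is correct and lowers the importance. None of these outputs, however, is a history-only percentage with ACT ≤ 19 or a history-only absolute score by visit.

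Last, the table shells are not in the documents, and titles do not show internal rows: Table 14.3.4.4.12 has no split in its title although 13.6.1 requires one. SAP 17.2.5.2 also asks for care over denominators in footnotes or programming notes. But for PEF the split is written in the text, and for ACT neither text nor title has one. Silence cannot be read as a split.

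**Conclusion.** The concern holds in a limited form. As specified, the by-visit absolute ACT score and percentage with ACT ≤ 19 rest on a denominator that changes after randomization and can differ by arm. Time trends and arm differences can be shifted either way: upward if de novo subjects score worse, which is plausible at diagnosis, and towards masking deterioration if they score better. The size is not derivable from the documents. Under the assumptions in Step 5 it is typically a few percentage points. Change from Baseline is unaffected as 13.6.2 is written, but it refers to different subjects from the other two rows. The tables are descriptive safety output, so no hypothesis test or primary result depends on them. Importance: minor to moderate.

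**What to change.** In SAP 13.6.2, state that ACT score, change from Baseline and percentage with ACT ≤ 19 are summarized in subjects with a medical history of asthma at screening, with n at each visit. Show de novo subjects in a separate row or listing from diagnosis onward. Split Tables 14.3.4.4.14 and 14.3.4.4.15 by asthma history, as is done for PEF. Because the only no-history subjects who take the ACT are those newly diagnosed, this one split separates exactly the two groups.

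The cost is a few lines of SAP text and the reprogramming of two tables. No new data are needed. The de novo group will probably be small, so counts or a listing will serve better than percentages there.

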13.7. Immunogenicity

Blood samples to assess anti-nemolizumab ADA will be collected at Baseline, Week 4, Week 8, and Week 16 of the Initial Period, and Week 24, Week 32, and Week 48 of the Maintenance Period and Follow-up visit. Immunogenicity analyses will be summarized for the Initial Period and the Maintenance Period on the PK population.

Details related to the processing of serum samples and the assessments of ADA will be described in the bioanalytical plan, which will be finalized before the beginning of sample analysis. Results will be described in the bioanalytical report, which will be included as an appendix in the final clinical study report.

Incidence of positive ADA results will be summarized (absolute occurrence and percent of subjects). The concentration of ADA titer (ng/mL) will be summarized as continuous variables. Neutralizing antibodies will be summarized with the number and percentage of the subjects.

The number and percentage of subjects with treatment related ADA will be summarized. A treatment-related ADA is defined when the Baseline screening or confirmatory ADA result is negative and the post-baseline confirmatory ADA result is positive.

This document is confidential.

14. Interim Analyses

No interim analysis is planned.

1.0

CD14152.SPR118161.SAP.V01

Approved 10-Nov-2022 00:00:00

This document is confidential.

15. Changes from Analysis Planned in Protocol

In protocol Section 8.4.9 (Prior and Concomitant Therapies), concomitant medications/therapies are defined as any therapies taken during the study (i.e., from the screening visit to the end of study).

However, for the analysis purpose, concomitant medications/therapies are defined as medications/therapies which start or stop or ongoing on or after the 1st injection of study drug.

1.0

CD14152.SPR118161.SAP.V01

Approved 10-Nov-2022 00:00:00

This document is confidential.

16. Reference List

Not applicable.

1.0

CD14152.SPR118161.SAP.V01

Approved 10-Nov-2022 00:00:00

This document is confidential.

17. Programming Considerations

All TFLs and statistical analyses will be generated using SAS® 9.4 or higher (SAS® Institute Inc., Cary, NC, USA). Computer-generated TFL output will adhere to the following specifications.

17.1. General Considerations

- A separate SAS program will be created for each output.
- Each output will be stored in a separate file.
- Output files will be provided in separate Word RTF and PDF format.
- Output files will be delivered in PDF format.
- The final TFLs will be provided in a combined PDF document including a table of contents which are hyperlinked to each output.
- Numbering of TFLs will follow International Conference on Harmonization (ICH) E3 guidance.

17.2. Table, Figure, and Listing Format

17.2.1. General

- All TFLs will be produced in landscape format, unless otherwise specified.
- All TFLs will be produced on paper size A4 using the Courier New font, size 8.
- The data displays for all TFLs will have a 0.8 inch (2cm) binding margin on top and bottom of a landscape oriented page and a minimum 0.3 inch (0.8cm) margin on the left and right sides.
- Headers and footers for figures will be in Courier New font, size 8.
- Legends will be used for all figures with more than 1 variable, group, or item displayed.
- TFLs will be in black and white (no color), unless otherwise specified.
- Specialized text styles, such as bolding, italics, borders, shading, and superscripted and subscripted text, will not be used in the TFLs, unless otherwise specified. On some occasions, superscripts 1, 2, or 3 may be used (see below).
- Only standard keyboard characters will be used in the TFLs. Special characters, such as non-printable control characters, printer-specific, or font-specific characters, will not be used. Hexadecimal-derived characters will be used, where possible, if they are appropriate to help display math symbols (e.g., μ). Certain subscripts and superscripts (e.g., cm², C_{max}) will be employed on a case-by-case basis.
- Mixed case will be used for all titles, footnotes, column headers, and programmer-supplied formats, as appropriate.

17.2.2. Headers

- All output should have the following header at the top left of each page:
 - Galderma Protocol RD.06.SPR.118161
 - Dry-run on dummy treatment/Draft/Final
- All output should have Page n of N at the top corner of each page. TFLs are internally paginated in relation to the total length (i.e., the page number should appear sequentially as page n of N, where N is the total number of pages in the table).
- The date output was generated should appear along with the program name as a footer on each page.

This document is confidential.

17.2.3. Display Titles

- Each TFL are identified by the designation and a numeral. (i.e., Table 14.1.1). ICH E3 numbering is strongly recommended, but sponsor preferences are obtained before final determination. A decimal system (x.y and x.y.z) are used to identify TFLs with related contents. The title is centered. The analysis population are identified on the line immediately following the title. The title and table designation are single spaced. A solid line spanning the margins will separate the display titles from the table.
- Column headers. There will be 1 blank line between the last title and the solid line.

Table x.y.z
 First Line of Title
 Second Line of Title if Needed
 ITT Population

